1.0 Introduction/Background

The prevalence of non-communicable diseases (NCDs) including diabetes, hypertension, heart failure and asthma is higher especially in the bottom income group. According to WHO and Ministry of Health (MOH) Malaysia 2020 report, expenditure for chronic diseases estimated involved around 0.65% of Malaysia's gross domestic product (GDP) which is about RM8.91 billion (Ministry of Health Malaysia, 2020). This showed that chronic diseases imposed a significant health burden to our country. Therefore, stakeholders and public should work together to identify the sources and curb the prevalence of chronic diseases from continuing to rise in Malaysia. Despite free access to essential medicines and health services in the public sector, health literacy remains poor, service uptake remains low, and medication non-adherence persists.

Adherence to therapies is a primary determinant of treatment success and is associated with improved clinical outcomes in the management of chronic diseases. Generally, the medication adherence rates are lower in chronic disease patients than in those with acute disease. Failure to adhere negatively affects the efficacy, safety and costs of therapies. According to the World Health Organization's (WHO's) 2003 report, 50% of patients with chronic diseases do not adhere to their prescribed treatment and identified non-compliance as global health crisis. Similarly, in Malaysia, despite the Malaysian population having good and easy access to effective medical therapy under the public healthcare system, approximately 46% to 56% of patients with hypertension were non-adherent in terms of their medications. Increasing medical adherence is, therefore, a public health priority.

The health ministry has tried various interventions aiming to improve medication adherence, including technical, behavioural, educational, social support and structural interventions. However, changing people's behaviours toward medication adherence can be challenging. To compound this problem, long-term care requires the active involvement of healthcare resources and is usually costly and labour-intensive. Thus, new and innovative approaches to changing the attitudes and behaviours regarding adherence are needed.

In Asia-Pacific countries, usually it is the families who are primarily and personally responsible for the healthcare of the patients due to the culture. Thus, it is crucial to include them as part of the solutions to the adherence issues. In the age of fourth industrial revolutions and the advancements of digital technologies, digital solutions such as applications ('apps') on

smartphones, are increasingly used in healthcare. Further, the extensive development of information and communication technologies characteristic of modern society enables interventions to reach large populations. CareAide® is a digital app that may help to manage complex medicine schedules and improve adherence thus help manage complex medicine schedules with minimal involvement of healthcare resources. The app can include both the patients and the caregivers to monitor the medication taking behavior.

Previous studies have shown the association of adherence and clinical outcomes in diabetes, hypertension, asthma and heart failure patients (Asche et. al. 2011; Chia et. al. 2021; Shang et. al. 2019; Vahatalo et. al. 2021). These studies have shown the improvement of glycaemic control, blood pressure, health care utilization, quality of life, mortality, cardiovascular events and asthma control with higher adherence. Therefore, by using the CareAide® app, we hypothesized that these important clinical and health-related quality of life outcomes will also be indirectly improved when the adherence increases.

Mobile health interventions have been proved to be cost-effective in the management of diabetes and hypertension in overseas studies (Li et al., 2021; Tsuji et. al., 2020; Purcell et al., 2014). However, a few systematic reviews found that the outcome for economic evaluation were inconsistent, and most studies reported applied simple platforms such as text messages or phone reminder (Beratarrechea et al., 2014, Iribarren et al., 2017; Li et al., 2020; Sanyal et al., 2018). Furthermore, there is little evidence regarding the economic evaluation of mobile health apps for improving chronic disease management in developing country such as Malaysia. Therefore, this study will also explore the economic impact of mHealth app (CareAide ®) in the management of chronic diseases among adults in Malaysia.

Despite the launch and its utility, it is important to understand how people perceive and use the digital app. The user satisfaction survey can provide a better understanding of users' perception of the CareAide® app. Through assessing users' perception and satisfaction with the app, it is possible to improve the design of future CareAide® app that is more effective and can tailor the features according to their needs. Therefore, this study also aims to gauge the perception and satisfaction of the CareAide® app. Findings from this study will be helpful for the app developers for revisiting their app features and services that can lead to continued use of the app.

2.0 Research Questions

1. Can CareAide® improve the medication adherence?

2. What is the clinical impact of CareAide® on chronic diseases?
3. What is the economical and HRQOL impact of CareAide®?
4. What is the users' perception on the CareAide® application?

3.0 Research Objective:

3.1 Primary Objective

1. To evaluate the effect of CareAide® intervention on adherence to medications in patients with chronic diseases.

3.2 Secondary Objectives

1. To determine the clinical outcomes of CareAide® usage in patients with chronic diseases.
2. To evaluate and determine the cost-effectiveness of CareAide® in the management of chronic diseases in Malaysia.
3. To study and assess the burden and health-related quality of life (HRQoL) of chronic diseases for estimation of the quality adjusted life years (QALY).
4. To gauge the users' perception and satisfaction of the CareAide® application.

4.0 Methodology

4.1 Study Design

A 3- and 6- month open-label multicentre randomized controlled trial with two parallel groups will be conducted. This study will take place in the outpatient setting of the three hospitals [i.e., Hospital Putrajaya, Hospital Pulau Pinang and Universiti Malaya Medical Center (UMMC)) in Malaysia]. Standard chronic disease treatments will be given to both groups of participants, but the CareAide ® app will be provided for the experimental group during the trial. Both groups will be allocated to 1:1 ratio. Randomization number will be generated by using online number generated programme. Consultants reviewing patients at medical, cardiology, diabetes mellitus and asthma clinics will provide referral and notify independent researchers for eligibility and group assignments. Eligible patients will then be instructed to see pharmacists/researchers at outpatient pharmacies to refill their prescriptions and subsequently enrol in the assigned study group either to receive an intervention with CareAide® or to receive normal clinical care. Information and training on the app will be provided by these researchers to the participants.

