4.2 Participant Recruitment, Eligibility Criteria and Study Procedures

Patients will be recruited at the respective outpatient clinics. At the usual care clinic appointments, patients have their demographics and baseline data of blood pressure, blood sugar, basic blood profiles, asthma control and review of their disease management collected by consultants/researchers. Patients who meet the study criteria will then be instructed to see pharmacists/researchers at outpatient pharmacy to refill their medications. The pharmacists/researchers will screen patients' inclusion and exclusion criteria for this study and will explain that they may or may not be selected for the study and if they agree, proceed to provide written informed consent. The adherence data from the screening will be collected to gauge the general adherence rate in these group of patients. An independent researcher, who is not involved in the intervention and control groups, will use the random number function in Excel to generate randomisation sequences. The random numbers will be placed in opaque envelopes, which subsequently will be opened by pharmacists/researchers at the outpatient pharmacies. Participants and pharmacists/researchers are unblinded to group assignment and are aware of the intervention, but the study hypotheses are not disclosed to the participants. The assessor and statisticians are blinded to participant allocation. The study will be evaluating usual care compared with usual care plus pharmacist-driven patient-specific adherence interventions - CareAide® medication adherence digital application. Usual care provided by these hospitals comprises clinic appointments every 3 to 6 months.

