4.2.2 Control group

- Control group will not be asked to download any digital applications but only receive the usual care by the hospitals.

4.3 Patients' inclusion and exclusion criteria are as follow:

4.3.1 Inclusion criteria:

- Age: 18 years and above
- Diagnosed with selected non-communicable diseases (NCDs): hypertension, diabetes mellitus, heart failure or asthma for at least 6 months
- Prescription generated from one of the following specialty clinics: Medical, Cardiology, Diabetes Mellitus or Asthma clinics
- Medications are prescribed in previous 3 months and refill at the point of recruitment
- Morisky Medication Adherence Scale (MMAS) score < 6
- More than three medications daily or two medications with multiple dosing intervals.
- One or more hospital admissions in the prior 24 months
- Understand and able to command in English and own a smartphone

4.3.2 Exclusion criteria:

- Medications prescribed from other institution providers
- Existing mobile health app or medication reminder app user
- Pregnant
- Cognitively impaired
- Prisoners
- Bed-bound
- Severe diseases/comorbidities – terminal cancer, psychiatry, etc

4.3.3 Withdrawal criteria:

Participants can choose to withdraw at any time for any reason, specified or unspecified, and without prejudice to their care. Participants may be withdrawn if the investigator feels that it is not for the participants' best interest to continue. The following is a list of possible reasons for study intervention discontinuation:

- Screening failure

- Participant withdrawal of consent
- Participant is not compliant with study procedures
- Protocol violation requiring discontinuation
- Lost to follow-up
- Request from sponsor for early termination of study
- Participant death

Withdrawn participants will not be replaced. It will be documented whether or not each subject completes the clinical study. If the Investigator becomes aware of any serious, related adverse events after the subject completes or withdraws from the study, they will be recorded in the source documents and on the Case Report Form (CRF). The Investigator will contact participants who are lost to follow-up. Contacts attempts with such subjects will be documented in the participant's records (e.g., times and dates of attempted phone contact, receipt for mailing a registered letter, etc.).

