4.5 Sample Size

The primary outcome for this study is to assess medication adherence of patient after using mobile health application. Therefore, sample size for this randomized controlled trial is calculated using the continuous outcome formula below (Charan & Biswas, 2013; Wittes, 2002):

$$n_i = \frac{2(Z_{\alpha/2} + Z_{\beta})^2 P (1 - P)}{(P_1 - P_2)^2}$$

n_i = sample size required for each group ($i = 1,2$)

$Z_{\alpha/2}$ = Assumed type I error: α equal to 5%, then $Z_{0.05/2} = Z_{0.025} = 1.96$ (From Z table)

Z_{β} = Assumed power of 80% $Z_{\beta}=0.84$

$P_1 - P_2$ = Effect Size= Difference in the proportion of events in two groups

P = Total prevalence

Total Sample size needed: 388 per group

Note: Based on few past studies reported for non-adherence rate for patients in Malaysia is within 46.6% to 56% (Ting et al., 2019). Therefore, assumption of prevalence of chronic disease is 70%

of the adult and adherence rate of 50% is made. A systematic review showed that mobile app able to improve adherence by 7% to 40% (Pérez-Jover et al., 2019). Medication non-adherence rate of 50% is expected in control group and 40% is expected in intervention group. For a 10% absolute difference in medication non-adherence rate between control and intervention group, 388 patients per arm should be recruited in the study assuming a type I error of 5% and power of 80%.

N (number to enrol) * (1-% drop out) = desired sample size

Therefore N (number to enrol) = desired sample size / (1- % drop out)

$N = 388 / 0.80 = 485$ per group

Based on a systemic review published by Wood and colleagues found out there is a possibility of 20% loss of follow-up, drop out and those who are unable to meet the inclusion criteria (Wood et al., 2004). Therefore, a minimum sample size of 970 is needed in this study, with the number of 485 in each arm.

The sample size obtained from the primary outcome is too large and which might need to spend more time and manpower. Hence, the sample size calculation is repeated with the use of secondary outcome which is cost-effectiveness economic evaluation of the study. Glick (2011) formula is applied for the calculation of sample size as it incorporates all important economic evaluation informations such as difference in treatment costs and effects and willingness to pay threshold in a single formula.

$$n_i = \frac{2 \left(Z_{\alpha/2} + Z_{\beta} \right)^2 \left(Sd_c^2 + (W^2 Sd_Q^2) - (2 W p Sd_c Sd_Q) \right)}{(W\Delta Q - \Delta C)^2}$$

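### Sections 4.1 and 4.2 disagree on whether groups are assigned before or after pharmacy screening and consent, and neither says the arm stays concealed until both are complete

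*Combined protocol and SAP*

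**What the plan says.** Section 4.1 (Study Design): consultants in the specialty clinics "will provide referral and notify independent researchers for eligibility and group assignments". Eligible patients then go to the outpatient pharmacy, where they "subsequently enrol in the assigned study group either to receive an intervention with CareAide® or to receive normal clinical care".

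Section 4.2 (Participant Recruitment, Eligibility Criteria and Study Procedures): pharmacists/researchers at the pharmacy screen against the criteria and tell patients that they "may or may not be selected for the study and if they agree, proceed to provide written informed consent". On the sequence it says: "An independent researcher, who is not involved in the intervention and control groups, will use the random number function in Excel". The numbers go into opaque envelopes, "which subsequently will be opened by pharmacists/researchers at the outpatient pharmacies". The section states that participants and pharmacists/researchers know the group, while the assessor and statisticians do not.

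Section 4.3.3 (Withdrawal criteria): "Screening failure" is the first listed reason for discontinuing the study intervention, and withdrawn participants are not replaced.

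Section 4.5 (Sample Size): in the calculation leading to 485 per arm, the 20% loss includes "those who are unable to meet the inclusion criteria".

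Section 4.6 (Data Analyses): an ITT analysis is named. The handling of a patient found ineligible after assignment is not described.

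**The concern.** Random allocation protects against selection bias only if whoever decides on eligibility and consent cannot know the next assignment. Read literally, 4.1 has the group settled at referral and enrolment following it. Section 4.2 has the group revealed at the pharmacy, after screening and consent. Both cannot be the procedure, and three hospitals could each follow a different one.

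The order matters here because MMAS < 6 is an entry criterion and MMAS-8 is also one of the two primary adherence measures. Someone scoring that scale with the arm known could influence both who enters and the baseline value. Screening failure as a reason for stopping the intervention adds to the doubt: in a trial that randomises only screened and eligible patients, it should not arise after assignment.

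**Working it through.** **Step 1. The two sequences side by side.**

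| Step | Section 4.1 | Section 4.2 |
|---|---|---|
| Eligibility | Raised at referral with independent researchers; eligible patients go on to the pharmacy | Patients meeting the criteria are sent to the pharmacy, where staff screen them |
| Consent | Not mentioned | Written consent, described after pharmacy screening |
| Group assignment | Named at referral, with eligibility | By envelope opened at the pharmacy |
| Enrolment | At the pharmacy, into the assigned group | At the pharmacy |
| Source of numbers | Online generator | Excel random number function |

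The sections differ on the timing of assignment and on the source of the random numbers.

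**Step 2. Where MMAS is scored.** The clinic data listed in 4.2 are demographics, blood pressure, blood sugar, blood profiles, asthma control and a disease review. MMAS is not among them. Adherence data are said to come from screening, which pharmacy staff carry out. So MMAS < 6 appears to be applied at the pharmacy, which under the 4.1 order falls after assignment.

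**Step 3. What 4.2 secures on its own.** The narrative order (screen, consent, open) is sound, and the sequence is generated independently. Three safeguards are not stated: that opening waits for completed screening and consent, that envelopes are sealed, and that they are sequentially numbered and used in order. One unblinded staff group screens, takes consent and opens the envelopes.

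**Step 4. The plan's own figures, for scale.** With non-adherence of 50% and 40%, P = 0.45 and the formula in 4.5:

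n = 2 × (1.96 + 0.84)² × 0.45 × 0.55 / 0.10² = 388.08, so 388 per arm; 388 / 0.80 = 485.

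The stated figures reproduce. They supply the 10-point yardstick used below; the procedural point does not depend on them.

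**Step 5. Illustration of possible bias.** No document figure measures this, so the inputs are assumptions: no true effect, 50% adherent in both arms (the plan's control rate), a fraction x of one arm left out with the arm known, and a proportion a of those left out who would have been adherent.

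Spurious difference = (0.50 − x·a) / (1 − x) − 0.50

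| x | a = 0 (worst case) | a = 0.20 | a = 0.50 (unselective) |
|---|---|---|---|
| 5% | 2.6 points | 1.6 points | 0 |
| 10% | 5.6 points | 3.3 points | 0 |
| 16.7% | 10.0 points | 6.0 points | 0 |
| 20% | 12.5 points | 7.5 points | 0 |

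For example, (0.50 − 0.10 × 0.20) / 0.90 − 0.50 = 0.033. The size depends entirely on how many are left out and how selectively.

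**The case against.** The strongest reply is that 4.2 is the procedural section and already has the right order. On that view 4.1 only gives the purpose of the notification, and enrolment in an assigned group fits assignment by envelope at the pharmacy. Opening of opaque envelopes by recruiting staff is not in itself a breach of concealment. Much of this stands: 4.1 never says that pharmacy staff learn the arm before they screen or take consent. It does not remove the conflict, because 4.1 pairs group assignment with eligibility at referral, and 4.2 does not make opening conditional on completed screening and consent.

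Four stronger readings are tempting and are not supported:

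- A reader might infer that staff do screen and take consent knowing the arm. That needs 4.1 to govern and the assignment to reach the pharmacy. Neither is stated.
- A reader might infer that the ITT analysis is broken. Section 4.3.3 concerns stopping the intervention, not leaving the analysis, and non-replacement is compatible with ITT. What is missing is a rule for ineligibility discovered late.
- A reader might infer that the 20% allowance behind the 200 patients also absorbs ineligible patients. That wording belongs to the 485-per-arm calculation, which the plan sets aside as too large. The step from 150 to 200 mentions attrition only.
- A reader might take the cited non-adherence range of 46.6% to 56% to mean that 44% to 53% of candidates (1 − 0.56 to 1 − 0.466) would fail screening after assignment. That equates cited non-adherence with MMAS < 6 and presumes screening follows assignment. The documents establish neither.

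Figure 1, the CONSORT flow chart, is not shown in the text available. It may already place screening before randomisation, so nothing here relies on its absence.

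**Conclusion.** The point holds as an unresolved conflict over the timing of allocation, together with concealment that 4.2 implies but does not secure. Selection with the arm known is a possibility under one reading, not a described practice. The screening-failure entry leaves room for exclusions after assignment, without showing that any would leave the analysis.

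The documents support no estimate of bias. Under the assumptions in the working, 10% selective exclusion from one arm gives 0 to 5.6 points against a planned difference of 10. This shows why the order matters and does not predict what would happen. Keeping everyone randomised in the analysis would guard against exclusion after assignment, but not against patients who are never enrolled because their arm was foreseen. Both parts therefore need attention. The change should be made before recruitment, since concealment cannot be restored afterwards.

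**What to change.** Rewrite 4.1 to match 4.2, with one sequence used at all three hospitals:

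1. Confirm eligibility, including MMAS < 6.
2. Obtain written consent.
3. Record baseline measures.
4. Write the participant's number on the next sealed, sequentially numbered opaque envelope.
5. Open the envelope.

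State that no envelope is opened until steps 1 to 4 are complete, and name one source of random numbers in both sections. Remove screening failure from the list in 4.3.3 and treat it as an event before randomisation. State in 4.6 that every randomised patient stays in the ITT analysis in the assigned group, including any later found ineligible. Check that Figure 1 agrees.

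The cost is protocol wording and numbered envelopes.

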4.2 Participant Recruitment, Eligibility Criteria and Study Procedures

Patients will be recruited at the respective outpatient clinics. At the usual care clinic appointments, patients have their demographics and baseline data of blood pressure, blood sugar, basic blood profiles, asthma control and review of their disease management collected by consultants/researchers. Patients who meet the study criteria will then be instructed to see pharmacists/researchers at outpatient pharmacy to refill their medications. The pharmacists/researchers will screen patients' inclusion and exclusion criteria for this study and will explain that they may or may not be selected for the study and if they agree, proceed to provide written informed consent. The adherence data from the screening will be collected to gauge the general adherence rate in these group of patients. An independent researcher, who is not involved in the intervention and control groups, will use the random number function in Excel to generate randomisation sequences. The random numbers will be placed in opaque envelopes, which subsequently will be opened by pharmacists/researchers at the outpatient pharmacies. Participants and pharmacists/researchers are unblinded to group assignment and are aware of the intervention, but the study hypotheses are not disclosed to the participants. The assessor and statisticians are blinded to participant allocation. The study will be evaluating usual care compared with usual care plus pharmacist-driven patient-specific adherence interventions - CareAide® medication adherence digital application. Usual care provided by these hospitals comprises clinic appointments every 3 to 6 months.

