4.4.1.2 Secondary outcomes

Fasting blood sugar, HbA1C, cardiovascular events (heart failure admission, mortality), asthma control and blood pressure, hospitalizations and emergency visits measurements will be based on the clinics attended by the participants. Health care utilization, quality of life and health care expenditures will be measured for all the participants.

i. Data Collection

Data on patients' sociodemographic, resources consumptions such as direct and indirect medical costs and health quality of life (HRQoL) will be collected.

ii. Sociodemographic

Data such as socio-demographics (age, sex, education level, occupation, income, and religion), will be collected via face-to-face interview or phone interview via a structured and validated questionnaire.

iii. Direct Medical Cost

This study will apply a bottom-up micro costing approach for direct cost estimation. Healthcare costs such as outpatient visits, medicine use, hospitalization, diagnostic and laboratory test costs will be gathered in this study for direct cost estimation of chronic diseases. Costs for outpatient visits, hospitalization, diagnostic and laboratory tests will be valued based on the MOH Full Paying Patient Tariff Schedule of fees for a foreigner patient scheme provided by the Financial Department for Ministry of Health Hospitals. Medication utilization costs will be estimated from the National Price List of Medicines provided by the Procurement Unit of the Pharmacy Department. Costs of medicine per patient will be calculated by total drugs supplied for a patient multiplied by the average acquisition cost price obtained of the hospital. All costs will be valued in Malaysia Ringgit (MYR).

iv. Indirect Medical Cost

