
$n_i =$ sample size required for each group ($i = 1,2$)

$Z_{\alpha/2} =$ Assumed type I error: α equal to 5%, then $Z_{0.05/2} = Z_{0.025} = 1.96$ (From Z table)

$Z_{\beta} =$ Assumed power of 80% $Z_{\beta} = 0.84$

$W =$ Willingness to pay threshold

$p =$ Expected correlation between difference in costs (ΔC) and effects (ΔQ)

$\Delta Q =$ Expected difference in mean effects

$\Delta C =$ Expected difference in mean costs

$Sd_Q =$ Expected standard deviation for the effects

$Sd_C =$ Expected standard deviation for the costs

To our knowledge, there is no published study has evaluated the direct and indirect costs and quality of life associated with mobile health app for the management of non-communicable diseases. Therefore, the calculation is based on the assumption and few literature results. According to a study published in Malaysia, RM 2499.15 is required for the managing of patient complicated with diabetes and heart failure after the first event (Shafie & Ng, 2020). The cost from the study is adjusted according to Consumer Price Index 2022. The cost difference between treatment group is considered as around 30% as reported by the use of mobile app in the management of heart failure study (Cano Martín et al., 2014). A minimum difference of 0.01 is estimated in term of QALY in favour of mobile health app user. Sd_c and Sd_Q are assumed as RM1000 and 0.01 respectively. The willingness to pay threshold is set at RM 28,470 per QALY as reported by Lim et al. (2017). The correlation coefficient is set at minimum 0.1 as estimated from cost-effectiveness analysis of a mobile-based intervention for patients with type 2 diabetes mellitus conducted by Li et al. (2021). A number of 150 patients (75 per study group) is required to detect at least 80% power assuming a two-tailed test and alpha of 5% between treatment group. The sample size will be rounded up to 200 patients to account for a possibility of 20% attrition. The sample size obtained is corresponding to the sample size applied in Li et al. (2021) cost-effectiveness analysis study.

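### Three hospitals and four clinics are pooled with no blocking, stratification or adjustment described, so chance differences in site and disease mix add avoidable noise to the comparisons

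*Combined protocol and SAP*

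**What the plan says.** Section 4.1 (Study Design) sets the ratio: "Both groups will be allocated to 1:1 ratio". The sequence is described twice, and differently. Section 4.1 says "Randomization number will be generated by using online number generated programme"; section 4.2 says that an independent researcher "will use the random number function in Excel to generate randomisation sequences". On concealment, section 4.2 says: "The random numbers will be placed in opaque envelopes, which subsequently will be opened by pharmacists/researchers at the outpatient pharmacies". No block, stratification factor, minimisation or separate list by hospital or clinic appears in the text.

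The population is mixed. Section 4.1: "This study will take place in the outpatient setting of the three hospitals". The inclusion criteria (4.3.1) add: "Prescription generated from one of the following specialty clinics: Medical, Cardiology, Diabetes Mellitus or Asthma clinics". Section 4.4.1.2 says of the clinical secondary outcomes that their "measurements will be based on the clinics attended by the participants"; utilisation, quality of life and expenditure are measured in everyone.

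Section 4.6 (Data Analyses) plans t, Mann-Whitney and chi-square or Fisher tests, ordinal logistic regression on the MMAS ranking, and linear regression for predictors of HRQoL. The ICER is the difference in cost between arms divided by the difference in QALYs, with bootstrapping. None of these is said to include hospital or clinic. Section 4.5 adopts 200 patients, from 75 evaluable per group.

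**The concern.** Hospital and disease clinic can plausibly affect cost, utilisation, quality of life and adherence. When such factors are pooled, a trial can balance them at allocation, adjust for them in the analysis, or do both. This plan describes neither. Any chance difference between the arms in the share of patients from a given clinic or hospital then passes straight into the unadjusted differences in adherence, cost, QALYs and utilisation.

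This matters more here because the sample was cut to 200 after the adherence calculation had given 970. In a trial of that size, precision that can be had almost free should not be left unused. The allocation part must be settled before the first patient is enrolled.

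**Working it through.** **The plan's own figure.** Section 4.5 gives z = 1.96 and 0.84, W = RM 28,470, QALY difference 0.01, cost SD RM1000, QALY SD 0.01, correlation 0.1, base cost RM 2499.15 and a cost difference of about 30%.
- Variance: 1000² + (28,470 × 0.01)² − 2 × 28,470 × 0.1 × 1000 × 0.01 = 1,024,114.
- Cost difference: 0.30 × 2499.15 = 749.745, taken as an added cost and before any price-index adjustment.
- n = 2 × 2.8² × 1,024,114 / (284.7 − 749.745)² = 74.25, so 75 per group.
- 150 / 0.80 = 187.5, so 188, which the plan rounds up to 200. The figure reproduces.

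The plan gives no figure for allocation imbalance. It also gives no clinic or hospital sizes; even splits (50 per clinic, about 67 per hospital) are my assumption.

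**Arm sizes under simple randomisation**, exact Binomial(n, 0.5):

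| Group | Split at least as uneven as | Probability |
|---|---|---|
| All 200 | 110:90 | 17.9% |
| All 200 | 120:80 | 0.6% |
| One clinic of 50 | 30:20 | 20.3% |
| At least one of four clinics | 30:20 | 1 − (1 − 0.203)⁴ = 59.6% |
| One hospital of 67 | 41:26 | 8.6% |
| At least one of three hospitals | 41:26 | 1 − (1 − 0.0864)³ = 23.8% |

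Smaller clinics fare worse: with 25 patients, a split of 60:40 or worse has probability 42.4%.

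**Arm sizes if a fixed 100:100 list is shuffled without strata.** The overall ratio is then exact. Within a clinic of 50 the count is hypergeometric, and 30:20 or worse has probability 14.1%. Counting all four clinics jointly, at least one is that uneven with probability 40.4%.

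**Power lost through unequal numbers.** Relative efficiency is 4ab/(a + b)².
- 30:20 gives 4 × 30 × 20 / 50² = 0.96; 32:18 gives 0.92; 110:90 gives 0.99.
- With 150 evaluable, the 95% limit of the split is 87:63. Economic power falls from 80.3% to 79.3%. Power for the adherence difference (50% against 40% non-adherent) falls from 23.2% to 22.6%.

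This loss is small.

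**Noise from disease mix.** The documents give no cost by disease, so this is an illustration. Let clinic explain a share R² of the variance of a cost with SD RM1000. The 95% bound on the shift in the cost difference due to chance mix alone, at 75 per arm, is 1.96 × √R² × 1000 × √(2/75), where √(2/75) = 0.1633.
- R² = 0.10: 1.96 × 316.2 × 0.1633 = RM101.
- R² = 0.40: 1.96 × 632.5 × 0.1633 = RM202.

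The planned cost difference is about RM750. Adjusting for clinic removes this part of the variance. The gain is equivalent to 1/(1 − R²) − 1 more patients: 11% at R² = 0.10 and 67% at R² = 0.40.

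**The case against.** The strongest reply is that this is a gap in reporting. A reader might infer that the trial uses unrestricted simple randomisation and so fails its 1:1 ratio. The documents do not support that: they do not say that the list is simple or unrestricted. The Excel function can equally shuffle a fixed 100:100 list or build blocks, and 1:1 can mean equal probability of allocation, which simple randomisation satisfies. This stands. But a shuffled list without strata still leaves 14% per clinic and about 40% for any of four, and the analysis section names no adjustment whichever list is used.

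A second reply is that a 30:20 split does almost no harm, and that chance imbalance is already reflected in the standard errors, p-values and bootstrap intervals. This also stands. The comparisons are not biased by design and the tests are not invalid. What remains is lost precision.

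Third, three premises that would make the point look worse are not in the documents: clinic groups of about 50, sharply different costs and event rates by disease, and formal comparisons within clinics. Section 4.4.1.2 can be read as saying only which outcomes are recorded for whom, and section 4.6 specifies no within-clinic test. I therefore treat 50 as an assumption and do not rely on the other two.

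Finally, stratifying by hospital and clinic together makes 12 strata of about 17 patients. The pharmacists/researchers who screen and take consent also open the envelopes and know the allocations, so small blocks in small strata would let them guess some assignments. This stands and has shaped the remedy.

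**Conclusion.** The point holds as one of avoidable imprecision and incomplete specification. No blocking, stratification or adjustment for hospital or clinic is described, and the two accounts of the generator disagree and must be reconciled. The consequence for power through unequal arm sizes is about one percentage point or less. The consequence through site and disease mix depends on how strongly clinic predicts the outcome, which the documents do not say. At an assumed 10–40% of cost variance it is a chance shift of about RM100–200 against a planned difference of about RM750. The split probabilities (20% and 60%, or 14% and about 40%) rest on even clinic sizes; uneven sizes would worsen the smaller clinics. None of this supports a claim that the planned tests are biased or invalid. If a restricted list is already intended, a sentence saying so settles the allocation half; the adjustment half remains.

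**What to change.** 1. Reconcile sections 4.1 and 4.2 so that one generator and one procedure are described.
2. Have the independent researcher prepare a separate list and labelled envelope set for each hospital, in permuted blocks of randomly varying size (for example 4 and 6), with the sizes withheld from the pharmacists/researchers. An incomplete block of 6 leaves a difference of at most 3, so the arms differ by at most 3 per hospital and 9 overall.
3. Include hospital and recruiting clinic as covariates in the between-arm models for adherence, cost, QALYs and utilisation. For the economic analysis, for example, estimate regression-adjusted incremental cost and QALY within each bootstrap replicate. Clinic is handled here and not as a second stratification factor, which avoids 12 small strata.

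Cost: a revised spreadsheet and three envelope sets before the first patient, a short addition to section 4.6 and a little more analysis work. The downside is slight predictability of allocation in an open-label trial, limited by varying and concealing the block sizes. If recruitment has already begun, step 3 can still be written in before the data are analysed.
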